12.1 Institutional Review Board/Ethics Committee approval

The protocol for this study has been designed in accordance with the general ethical principles outlined in the Declaration of Helsinki. The review of this protocol by the IRB/EC and the performance of all aspects of the study, including the methods used for obtaining informed consent, must also be in accordance with principles enunciated in the declaration, as well as ICH Guidelines, Title 21 of the Code of Federal Regulations (CFR), Part 50 Protection of Human Subjects and Part 56 Institutional Review Boards.

The Investigator will be responsible for preparing documents for submission to the relevant IRB/EC and obtaining written approval for this study. The approval will be obtained prior to the initiation of the study.

The approval for both the protocol and informed consent must specify the date of approval, protocol number and version, or amendment number.

Any amendment to this protocol must be agreed to by the Principal Investigator and reviewed by Celgene. Amendments should only be submitted to IRB/EC after consideration of Celgene

review. Written verification of IRB/EC approval will be obtained before any amendment is implemented. The Investigator is also responsible for notifying the IRB/EC of any serious deviations from the protocol, or anything else that may involve added risk to subjects.

Any advertisements used to recruit subjects for the study must be reviewed and approved by the IRB/EC prior to use.

The Investigator should ensure that all persons assisting with the study are adequately informed about the protocol, amendments, study treatments, as well as study-related duties and functions.

The Investigator should maintain a list of Sub-investigators and other appropriately qualified persons to whom he or she has delegated significant study-related duties.

12.2 Informed consent

The Investigator must obtain informed consent of a subject or his/her designee prior to any study related procedures as per GCPs as set forth in the CFR and ICH guidelines.

Documentation that informed consent occurred prior to the subject's entry into the study and the informed consent process should be recorded in the subject's source documents. The original consent form, signed and dated by the subject and by the person consenting the subject prior to the subject's entry into the study, must be maintained in the Investigator's study files.

12.3 Subject confidentiality

Celgene affirms the subject's right to protection against invasion of privacy. In compliance with United States federal regulations, Celgene requires the Investigator to permit Celgene's representatives and, when necessary, representatives of the FDA or other regulatory authorities to review and/or copy any medical records relevant to the study in accordance with local laws.

Should direct access to medical records require a waiver or authorization separate from the subject's statement of informed consent, it is the responsibility of the Investigator to obtain such permission in writing from the appropriate individual.

12.4 Study records requirements

The Investigator must ensure that the records and documents pertaining to the conduct of the study and the distribution of the study drug, that is copies of CRFs and source documents (original documents, data, and records [e.g., hospital records; clinical and office charts; laboratory notes; memoranda; subject's diaries or evaluation checklists; pharmacy dispensing records; recorded data from automated instruments; copies or transcriptions certified after verification as being accurate copies; microfiches; photographic negatives, microfilm, or magnetic media; x-rays; subject files; and records kept at the pharmacy, at the laboratories, and at medico-technical departments involved in the clinical study; documents regarding subject treatment and study drug accountability; original signed informed consents, etc.]) be retained by the Investigator for as long as needed to comply with national and international regulations (generally 2 years after discontinuing clinical development or after the last marketing

approval). The Investigator agrees to adhere to the document/records retention procedures by signing the protocol.

12.5 Premature discontinuation of study

12.5.1 Single center

The responsible local clinical Investigator as well as Celgene have the right to discontinue this study at any time for reasonable medical or administrative reasons in any single center. Possible reasons for termination of the study could be but are not limited to:

- Unsatisfactory enrollment with respect to quantity or quality.
- Inaccurate or incomplete data collection.
- Falsification of records.
- Failure to adhere to the study protocol.

12.5.2 Study as a whole

Celgene reserves the right to terminate this clinical study at any time for reasonable medical or administrative reasons.

Any possible premature discontinuation would be documented adequately with reasons being stated, and information would have to be issued according to local requirements (e.g., IRB/EC, regulatory authorities, etc.).

13 REGISTRATION GUIDELINES

13.1 Study Registration

Registration will be done centrally at UC Davis. To register a patient, the site's data manager must complete the Eligibility Checklist and FAX a copy of this and the informed consent including the Bill of Rights to the Clinical Trials Support Unit/UC Davis Comprehensive Cancer Center

If there are any questions, contact CTSU

After verifying the eligibility; the CTSU Coordinator will register the patient onto the study and assign a patient accession number. See Appendix, ("Registration Procedures for Phase II Trials") for details.

13.2 Protocol Deviations

Study deviations and exceptions are not allowed. However, should the need arise, any deviation or exceptions should be reviewed by the site PI and coordinating center PI before they are enacted. If it does occur, it should be reported to the PI of the study within one week. Any consequences from deviations and exceptions must be reported to the University of California Davis Institutional Review Board as well as to local IRBs.

14 RECORDS TO BE KEPT AND DATA SUBMISSION SCHEDULE

14.1 Confidentiality of Records

The original data collection forms will be stored at the originating institution. The forms will be stored in a secure location.

14.2 Patient Consent Form

An original signed and dated participant Informed Consent document will reside in a secured location within the UCD CTSU or participating site. Copies of the signed and dated Informed Consent document will be provided to the study participant and UCD Health System Information Management for inclusion in the participant's UCD Health System Medical Record or per participating site's institutional policies.

14.3 Quality Assurance and Control

Quality assurance audits of select patients and source documents may be conducted by the UC Davis Cancer Center Quality Assurance Committee as outlined in the UC Davis Cancer Center Data and Safety Monitoring plan.

Quality control will be maintained by the CTSU Quality Assurance team according to CTSU policy.

Quality assurance audits may be accomplished in one of two ways: (1) source documents and research records for selected patients are mailed/sent by from participating sites to the Coordinating Center for audit, or (2) selected patient records may be audited on-site at participating sites. If the sponsor/PI chooses to have an audit at the Coordinating Center, then the Coordinating Center is responsible for having all source documents, research records, all IRB approval documents, Drug Accountability Record forms, patient registration lists, response assessment scans, x-rays, etc. available for the audit.

All study participants must be registered into the mandatory Revlimid REMSTM program, and be willing and able to comply with the requirements of Revlimid REMSTM. Females of reproductive potential must adhere to the scheduled pregnancy testing as required in the Revlimid REMS® program.

Criteria for females of childbearing potential (FCBP)

This protocol defines a female of childbearing potential as a sexually mature female who: 1) has not undergone a hysterectomy or bilateral oophorectomy or 2) has not been naturally postmenopausal (amenorrhea following cancer therapy does not rule out childbearing potential) for at least 24 consecutive months (i.e., has had menses at any time in the preceding 24 consecutive months).

The investigator must ensure that:

- Females of childbearing potential comply with the conditions for pregnancy risk minimization, including confirmation that she has an adequate level of understanding.
- Females NOT of childbearing potential acknowledge that she understands the hazards and necessary precautions associated with the use of lenalidomide
- Male patients taking lenalidomide acknowledge that he understands that traces of lenalidomide have been found in semen, that he understands the potential teratogenic risk if engaged in sexual activity with a female of childbearing potential or pregnant female, and that he understands the need for the use of a condom even if he has had a vasectomy, if engaged in sexual activity with a female of childbearing potential or pregnant female.

Contraception

Females of childbearing potential (FCBP) enrolled in this protocol must agree to use two reliable forms of contraception simultaneously or to practice complete abstinence from heterosexual intercourse during the following time periods related to this study: 1) for at least

28 days before starting lenalidomide; 2) throughout the entire duration of lenalidomide treatment; 3) during dose interruptions; and 4) for at least 28 days after lenalidomide discontinuation.

The two methods of reliable contraception must include one highly effective method and one additional effective (barrier) method. FCBP must be referred to a qualified provider of contraceptive methods if needed. The following are examples of highly effective and additional effective methods of contraception:

- o Highly effective methods:
 - Intrauterine device (IUD)
 - Hormonal (birth control pills, injections, implants)
 - Tubal ligation
 - Partner's vasectomy
- Additional effective methods:
 - Male condom
 - Diaphragm
 - Cervical Cap

Because of the increased risk of venous thromboembolism in patients with multiple myeloma taking lenalidomide and dexamethasone, combined oral contraceptive pills are not recommended. If a patient is currently using combined oral contraception the patient should switch to one of the effective method listed above. The risk of venous thromboembolism continues for 4–6 weeks after discontinuing combined oral contraception. The efficacy of contraceptive steroids may be reduced during co-treatment with dexamethasone.

Implants and levonorgestrel-releasing intrauterine systems are associated with an increased risk of infection at the time of insertion and irregular vaginal bleeding. Prophylactic antibiotics should be considered particularly in patients with neutropenia.

Pregnancy testing

Medically supervised pregnancy tests with a minimum sensitivity of 50 mIU/mL must be performed for females of childbearing potential, including females of childbearing potential who commit to complete abstinence, as outlined below.

Before starting lenalidomide

Female Patients:

FCBP must have two negative pregnancy tests (sensitivity of at least 50 mIU/mL) prior to prescribing lenalidomide. The first pregnancy test must be performed within 10-14 days prior to prescribing lenalidomide and the second pregnancy test must be performed within 24 hours prior to prescribing lenalidomide. The patient may not receive lenalidomide until the Investigator has verified that the results of these pregnancy tests are negative.

Male Patients:

Must agree to practice complete abstinence or agree to use a condom during sexual contact with pregnant females or females of childbearing potential throughout the entire duration of lenalidomide treatment, during dose interruptions and for at least 28 days following lenalidomide discontinuation, even if he has undergone a successful vasectomy.

During study participation and for 28 days following lenalidomide discontinuation

Female Patients:

- FCBP with regular or no menstrual cycles must agree to have pregnancy tests weekly for the first 28 days of lenalidomide treatment, including dose interruptions, and then every 28 days throughout the remaining duration of lenalidomide treatment, including dose interruptions, at lenalidomide discontinuation, and at Day 28 following lenalidomide discontinuation. If menstrual cycles are irregular, the pregnancy testing must occur weekly for the first 28 days of lenalidomide treatment, including dose interruptions, and then every 14 days throughout the remaining duration of lenalidomide treatment, including dose interruptions, at lenalidomide discontinuation, and at Day 14 and Day 28 following lenalidomide discontinuation.
- At each visit, the Investigator must confirm with the FCBP that she is continuing to use two reliable methods of birth control at each visit during the time that birth control is required.
- If pregnancy or a positive pregnancy test does occur in a study patient, lenalidomide must be immediately discontinued.
- Pregnancy testing and counseling must be performed if a patient misses her period or if her pregnancy test or her menstrual bleeding is abnormal. Lenalidomide treatment must be temporarily discontinued during this evaluation.
- Females must agree to abstain from breastfeeding during study participation and for at least 28 days after lenalidomide discontinuation.

Male Patients:

• Must practice complete abstinence or use a condom during sexual contact with pregnant females or females of childbearing potential throughout the entire duration of

lenalidomide treatment, during dose interruptions and for at least 28 days following lenalidomide discontinuation, even if he has undergone a successful vasectomy.

- If pregnancy or a positive pregnancy test does occur in the partner of a male study patient during study participation, the investigator must be notified immediately.
- Male patients should not donate blood, semen or sperm during therapy or for at least 28 days following discontinuation of lenalidomide.

Additional precautions

- Patients should be instructed never to give lenalidomide to another person.
- Patients should not donate blood during therapy and for at least 28 days following discontinuation of lenalidomide.
- Only enough lenalidomide for one cycle of therapy may be prescribed with each cycle of therapy.
- Any unused lenalidomide must be returned as instructed through Revlimid REMS™ program.

Appendix II ECOG Performance Status Scale

SCORE	DESCRIPTION	
0	Fully active, able to carry on all pre-disease performance without restriction.	
1	Restricted in physically strenuous activity but ambulatory and able to carry out work of a light or sedentary nature, e.g., light house work, office work.	
2	Ambulatory and capable of all self-care but unable to carry out any work activities. Up and about more than 50% of waking hours.	
3	Capable of only limited self-care, confined to bed or chair more than 50% of waking hours.	
4	Completely disabled. Cannot carry on any self-care. Totally confined to bed or chair.	
5	Dead.	

Appendix III

Cockcroft-Gault estimation of CrCl:

Cockcroft-Gault estimation of creatinine clearance (CrCl): (Cockcroft, 1976; Luke 1990)

CrCl (mL/min) = $(140 - age) \times (weight, kg)$ (Males) 72 x (serum creatinine, mg/dL)

 $CrCl (mL/min) = \underbrace{(140 - age) \times (weight, kg)}_{} \times 0.85$

(Females) 72 x (serum creatinine, mg/dL)

Appendix IV

NCI CTC Version 4.0

TOXICITY WILL BE SCORED USING NCI CTCAE VERSION 4.0 FOR TOXICITY AND ADVERSE EVENT REPORTING. A COPY OF THE NCI CTC VERSION 4.0 CAN BE DOWNLOADED FROM THE CTEP HOMEPAGE: (http://ctep.info.nih.gov or http://evs.nci.nih.gov/ftp1/ctcae/about.html). All appropriate treatment areas have access to a copy of the ctcae version 4.0

Appendix V

Rituxan® (Rituximab) Package Insert

This can be obtained at:

http://www.gene.com/gene/products/information/pdf/rituxan-prescribing.pdf

Appendix VI

Revlimid® (Lenalidomide) Package Insert

This can be obtained at:

http://www.revlimid.com/pdf/REVLIMID_PI.pdf

Appendix VII

Registration Procedures for Phase II Trials

REGISTRATION POLICIES

- A. Registrations for this protocol must be made through the Clinical Trials Support Unit (CTSU) of the University of California, Davis Cancer Center between the hours of 9am and 3pm (Pacific Time), Monday through Friday (except holidays). Documentation of current IRB approval of this protocol by non-UCD institutions must be on file prior to registration of patients at these institutions.
- B. Pre-study laboratory tests, scans, and x-rays, must be completed prior to registration, within the time frame specified in the protocol. The eligibility checklist must be completed. Patients must sign an informed consent prior to registration.
- C. If the patient is to be registered the same day as the proposed treatment start date, the UC Davis Protocol Coordinator must be notified 24 hrs prior to proposed treatment start date that the site has a patient to register.
- D. Patients may be registered up to 72 hrs prior to treatment initiation. The signed consent, completed checklist and reports from all pre-study laboratory tests, scans and x-rays must be faxed to the University of California, Davis Cancer Center Clinical Trials Support Unit in order to register the patient. The UC Davis Protocol Coordinator will review these documents and fax a registration confirmation within 3 hours. **NOTE:** Administration of study medication may not be initiated until the registration confirmation has been received.
- E. A patient failing to meet all protocol requirements may not be registered. If you have any questions regarding eligibility, please contact the coordinating site PI or Study Coordinator.

REGISTRATION PROCEDURES

If the patient is be registered the same day as the proposed treatment start date, the UC Davis Protocol Coordinator must be notified by fax 24 hrs prior to proposed treatment start date that the site has a patient to register. Patients may be registered up to 72 hrs prior to treatment initiation. The signed consent, completed checklist and reports from all pre-study laboratory tests, scans and x-rays must be faxed to the University of California, Davis Cancer Center Clinical Trials Support Unit in order to register the patient.

The Protocol Coordinator will verify that the patient is eligible, that pre-study tests have been completed, and that the forms are complete. The Protocol Coordinator will then register the patient, confirm the dose-level and assign a patient accession number. The Protocol Coordinator will fax back a registration confirmation including the patient's dose level and patient accession number within 3 hours.

NOTE: Administration of study medication may not be initiated until the registration confirmation has been received.

Appendix VIII

Data Collection Forms and Submission Schedule

All data will be collected using the UCD Database System (eVELOS) forms. All data forms will be completed, submitted and processed in accordance with UCD CTSU policies. Any and all source documentation should be maintained.

- ➤ SUBMIT WITHIN 24 HOURS OF REGISTRATION: Patient Registration Form
- ➤ SUBMIT WITHIN 14 DAYS OF REGISTRATION: In-House Pre-Study Evaluation Form (IH-102)
- > SUBMIT WITHIN 7 DAYS OF SCREENING FAILURE: Patient Screen Failure Form
- ➤ SUBMIT WITH 14 DAYS OF CYCLE COMPLETION: Adverse Event/Drug Relationship Form
- ➤ SUBMIT WITHIN 14 DAYS OF END OF EACH TREATMENT CYCLE: In-House Treatment Cycle Form (IH-201)
- ➤ SUBMIT WITHIN 14 DAYS OF EACH RESPONSE ASSESSMENT: Tumor Measurement Log
- ➤ SUBMIT WITHIN 14 DAYS OF OFF TREATMENT: Off Treatment/In Follow-up/Off Study/Expiration Form (IH-301)
- SUBMIT WITHIN 14 DAYS OF KNOWLEDGE OF DEATH IF PATIENT IS STILL ON STUDY OR 30-DAYS IF OFF STUDY:
 Off Treatment/In Follow-up/Off Study/Expiration Form (IH-301)
- ➤ SUBMIT WITHIN 2 DAYS OF KNOWLEDGE OF PROTOCOL DEVIATION: Clinical Trials Support Unit: Notice of Protocol Deviation
- ➤ SUBMIT WITHIN 14 DAYS OF EACH REQUIRED FOLLOW-UP ENCOUNTER: Follow-Up Form (IH-302)
- ➤ ALL SERIOUS ADVERSE EVENTS MUST BE REPORTED AS OUTLINED IN THE PROTOCOL.

Appendix IX

Correlative Studies (Instructions for Sutter Pacific Medical Foundation):

- 1. Three tubes of EDTA blood (10-ml each) and One serum tube, collected at the time-points per protocol.
- 2. Ship to UC Davis overnight, in ambient shipper with cool packs inside (not frozen packs)

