5.3 Overall design

The study is a phase II clinical trial with all patients to be accrued at UCD Cancer Center and other participating centers. All patients who are eligible will receive both lenalidomide and rituximab.

- Lenalidomide will be started at 20 mg daily, days 1-21 of a 28 day cycle.
- A total of 30 patients will be evaluated in this study.
- Rituximab 375 mg/m2/wk x 4 weeks, to begin on day 15 of cycle 1. After 4 cycles of therapy if a patient has not achieved a CR, the patient will be given a second course of Rituximab, on days 1, 8, 15 and 22 of cycle 5.

Patients who progress through this combination will be offered optional participation in a radiotherapy cohort. Up to 10 patients who consent will continue lenalidomide and receive local radiotherapy to a single target lesion.

- Lenalidomide will be continued at the patient's most recent dose daily, days 1 21 of a 28 day cycle.
- Radiotherapy will be delivered to a single involved site to a dose of 20 Gy over 5 daily fractions of 4 Gy each, day 1-5, using electron or photon beams with a conventional linear accelerator.

Investigational Drugs

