11.5 Sample Procurement for Immunologic Assessment

If a patient has consented and agreed to allow their blood to be used for research studies, 7-10 mL of whole blood in one purple top tube, 8mL in one BD vacutaner CPT cell preparation tube, and 7-10 mL in a serum separator tube will be acquired at the following timepoints: prior to treatment, and at day 15, 30, 60, and 120 and at the completion of treatment. Samples will be held on ice, centrifuged at 2500 RPM for 10 min, separated as soon as possible, and aliquoted into one (Preferably two) vials containing 0.1 – 0.5 mL serum each and two vials with the cellular contents. The cellular material obtained from the CPT tubes by removing the top layer (according to the manufacturers recommendations) and will be mixed with an equal part of freezing solution (30% DMSO + 70% fetal calf serum). The tubes will be labeled with a nonpatient identifying ID number with the date of collection, protocol number, and source and intended use of the material (i.e., plasma sample for cytokine assays). Sample volumes between 0.05 and 0.1 mL are acceptable, but the laboratory will not be able to repeat the analysis or further dilute the sample, if necessary. Samples will be frozen at -70°C batched and archived. Immune assessment will be done as described below. If there are any questions with sample procurement please page the study PI ([name])

11.6 CORRELATIVE STUDIES.

In this Phase II clinical trial the immunological affects of the combination of Lenalidomide and Rituximab in patients with previously untreated indolent NHL will be explored.

Rationale:

This clinical study will be a unique opportunity to measure and characterize the baseline immune parameters and immune modulating effects of lenalidomide with or without rituximab in patients with previously untreated indolent NHL. This will allow for a better understanding of the mechanism of action, better prediction of who will respond to treatment, and allow for rational design of future clinical trials with these and/or other biologics.

Objectives:

Comprehensive assessment of immune parameters prior to therapy, after treatment with lenalidomide alone, and after treatment with the combination of lenalidomide and rituximab

Assay timeline:

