The culture supernatants will be collected prior to addition of [3 H] thymidine and stored at -70°C. The supernatants will be assayed for several cytokines/chemokines (e.g. IL-2, IFN- γ , IL-17, IL-10, IL-4, TNF- α , TGF- β) using the Multiplex Bead-based Luminex® Technology, Cytokine Human 10-Plex Panel (or if batched with other samples, the Cytokine Human 25-Plex Panel) (Invitrogen, Carlsbad, CA), see below.

CTL activity will be assessed by using the ELISpot Assay Kit (R&D Systems, Minneapolis, MN) by measuring IFN-gamma producing CD8+T cells, per the manufacturer's recommendations.

Table 1: Phenotypic markers for analysis of various immune cells

Cell subset		Phenotype marker
T cell	CD4 ⁺ helper T cell	CD3 ⁺ CD4 ⁺
	CD8 ⁺ cytotoxic T cell	CD3 ⁺ CD8 ⁺
	Regulatory T cells	CD3 ⁺ CD4 ⁺ CD25 ⁺ Foxp3 ⁺
	Naïve T cell	CD4 ⁺ /CD8 ⁺ CD45RA ⁺ CD11a ⁺
	Memory T cell	CD4 ⁺ /CD8 ⁺ CD45RO ⁺ CD11a ⁺
	NK T cell	CD3 ⁺ CD56 ⁺ CD16 ⁺
	iNKT cell	CD3 ⁺ CD56 ⁺ CD16 ⁺ 6B11 ⁺ CD1d ⁺
NK cell		CD3 ⁻ CD56 ⁺ CD16 ⁺
B cell	B2 cell	CD19 ⁺ IgD ⁺ CD11b ⁻ CD5 ⁻
	B1a cell	CD19 ⁺ IgM ⁺ CD11b ⁺ CD5 ⁺
	B1b cell	CD19 ⁺ IgM ⁺ CD11b ⁺ CD5 ⁻
Dendritic cell	Myeloid DC	CD11c ⁺ HLADR ⁺ lymphomononuclear cell
		lineage negative
	Plasmacytoid DC (pDC)	CD123 ⁺ BCDA2/BCDA4 ⁺ HLADR ⁺
		lymphomononuclear cell lineage negative

T-reg Cells Function: CD4⁺CD25⁺ FoxP3⁺T cells will be isolated using magnetic separation with the MACS CD4⁺CD25⁺ isolation kit (Miltenyi Biotec, Auburn, CA) and then cultured with CD4⁺CD25⁻T cells in plates coated with anti-CD3/CD28 antibodies (5 µg/ml each) in the presence of Lenalidomide, or saline (control) for 3 days. The supernatant will be collected before the addition of [³H] thymidine for measurement IL-10, IL-4, TGF-β, IL-2, TNF-α, and IFN-γ by multi-parameter Hi-D FACS analyses or Multiplex Bead-based Luminex® Technology. Proliferation will be measured after 72h in culture, with [³H] thymidine labeling for the last 16 hours.

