A B cell functional assay will be performed by measuring IgM production using B cells isolated from blood. CD19⁺ B cells will be isolated by positive selection using magnetic beads (2). B cell subsets will be sorted by FACS. B cell will be stimulated by LPS or CpG for 3 days, then IgM production will be measured by ELISA [41].

Immunoglobulin Levels: Serum samples will be obtained at various time points to assess for the serum levels of IgM, IgA, and IgG. Immunoglobulin levels will be measured by the clinical lab at UCDMC using standard techniques.

NK, NKT and iNKT cell phenotype and functional assay: Human iNKT cells will be identified using CD1d tetramer and a novel monoclonal antibody (clone 6B11) specific for the CDR3 loop of the human $V\alpha24J\alpha18$ TCR alpha chain which specifically identify iNKT cells. Other antibodies comprise CD3-APC, CD4-PerCP and CD8 α -FITC (BD Biosciences, San Jose, CA). For surface staining, cells will be washed with staining buffer (PBS with 2% FCS), and incubated for 30 minutes, on ice in the dark with the relevant antibody combinations. Cells will then be washed twice with staining buffer and analyzed by flow cytometry (BD Coulter). Data will be collected using a FACS ARIA (BD Biosciences) and analyzed by "Flowjo" flow cytometry data analysis software (Tree Star Inc, Ashland, OR).

NK (CD3-CD56+CD16+), NKT (CD3+CD56+CD16+) and iNKT cells will be sorted from blood. The sorted NK/NKT cells will be stimulated with poly IC for 12 and 24 h. iNKT cells will be stimulated with iNKT cell-specific ligand, α-GalCer. Supernatants will be collected to analyze the levels of IFN-gamma, IL-6 and IL-8 using the BD cytometric bead array kit per the manufacturer's recommendations. IFN-gamma and IL-4 will be measured by CBA kit or intracellular staining. Sera cytokine will be measured by CBA kit.

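### Immune samples from one site are handled differently, cytokine kits are not fixed, and the planned unpaired t test accounts for neither

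*Combined protocol and SAP*

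**What the plan says.** **Collection and handling.** Section 5.3 has "all patients to be accrued at UCD Cancer Center and other participating centers". Section 11.5 sets out the general procedure: "7-10 mL of whole blood in one purple top tube, 8mL in one BD vacutaner CPT cell preparation tube", plus a serum separator tube. It continues: "Samples will be held on ice, centrifuged at 2500 RPM for 10 min, separated as soon as possible". Cells come from the CPT tube ("The cellular material obtained from the CPT tubes by removing the top layer"), are mixed with freezing solution, and are frozen, batched and archived.

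Appendix IX gives one participating site two instructions. The first is "Three tubes of EDTA blood (10-ml each) and One serum tube" at the protocol time points. The second is "Ship to UC Davis overnight, in ambient shipper with cool packs inside (not frozen packs". Nothing else is listed.

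**Kits.** In section 11.6, T-cell culture supernatants go on the "Cytokine Human 10-Plex Panel (or if batched with other samples, the Cytokine Human 25-Plex Panel". T-reg supernatants go to FACS or Luminex, with no rule for choosing. The serum cytokine paragraph names a Luminex assay of 37 analytes. The later paragraph on NK, NKT and iNKT cells says "Sera cytokine will be measured by CBA kit".

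**Objective and analysis.** Section 5.1.2 makes it a secondary objective to assess immune changes from before to after treatment and relate them to response. Section 5.2.2 lists serum cytokines as a secondary endpoint. The statistical paragraph at the end of section 11.6 names an unpaired Student's t test for lymphocyte frequency and function. It does not define the groups and has no term for site, batch or kit.

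**The concern.** Cytokine levels and functional assay results can depend on the time from draw to separation and on the kit used. The plan's own call for ice and prompt separation treats handling as relevant.

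There are two distinct problems. First, if the overnight-shipped samples read systematically higher or lower, that difference goes straight into an unpaired comparison that ignores site. It widens the spread and, if responders and non-responders come from the sites in different proportions, it looks like an association with response. Second, if a patient's visits are run on different kits, the kit offset looks like a treatment effect.

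At stake is the reading of the secondary immune results, in at most 30 patients and only those who consent to sampling.

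**Working it through.** **1. The two procedures side by side**

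| Item | Section 11.5 | Appendix IX |
|---|---|---|
| Tubes for cells or plasma | 1 purple-top (7-10 mL) + 1 CPT (8 mL) = 15-18 mL | 3 EDTA × 10 mL = 30 mL |
| Serum | 1 separator tube (7-10 mL) | 1 serum tube |
| CPT tube | yes | none listed |
| Before storage or shipping | ice, centrifuge, separate, freeze | no step listed |
| Transport | not described | overnight, cool packs |

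The CPT top-layer step of section 11.5 cannot be done on samples drawn under Appendix IX. EDTA is not in itself the difference if the purple-top tube is EDTA. The differences are the missing CPT tube, the number of tubes, and overnight transit in place of prompt separation. No section reconciles the two, sets a limit on time to processing, or requires that time to be recorded.

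**2. Effect of a site shift on pooled levels**

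The documents give no sample size or power for the immune analysis, so there is no planned figure to reproduce. Patients per site and the handling shift are also not given. Assume a share s of patients at the shipping site and a shift of D within-site SDs. With site ignored, the variance is multiplied by 1 + s(1−s)D², and the effective-sample fraction is the reciprocal.

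- s = 0.2, D = 0.25: 1 + 0.16 × 0.0625 = 1.01; fraction 0.99
- s = 0.3, D = 0.5: 1 + 0.21 × 0.25 = 1.0525; fraction 0.95
- s = 0.2, D = 1: 1 + 0.16 × 1 = 1.16; SD × 1.077; fraction 0.86
- s = 0.3, D = 2: 1 + 0.21 × 4 = 1.84; SD × 1.356; fraction 0.54

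**3. Unpaired against paired analysis of change**

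This is a simulation with 20,000 runs per setting. N = 30 comes from section 5.3. The other inputs are assumed: true change 0.5 SD, within-patient correlation 0.6, one third of patients at the shipping site, and the same site shift at both visits.

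| Site shift (SD) | Power, unpaired | Power, paired |
|---|---|---|
| 0 | 47% | 85% |
| 0.5 | 43% | 84% |
| 1.0 | 35% | 84% |
| 1.5 | 23% | 85% |

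A constant shift cancels within the patient. It does harm here only because the named test is unpaired.

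**4. Responders against non-responders, levels, site ignored**

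Assume 24 against 6 patients, no true difference, and a nominal 5% level. The bias is the shift times the difference in site shares, for example 1.0 × (4/6 − 6/24) = 0.42 SD.

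| Site shift (SD) | Equal shares (33%): false positives | Shares 25% vs 67%: false positives | Bias (SD), unequal shares |
|---|---|---|---|
| 0.5 | 4.4% | 6.4% | 0.21 |
| 1.0 | 3.2% | 10.6% | 0.42 |
| 1.5 | 1.7% | 14.6% | 0.63 |

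With equal shares there is no bias, and the test becomes conservative and loses sensitivity. Bias needs an unequal site mix.

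**5. Kit change between visits, paired test, no true change**

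Same 30 patients and correlation 0.6. An assumed kit offset of 0.25 SD gives 11% false positives if half the patients change kit and 31% if all do. An offset of 0.5 SD gives 29% and 84%. Pairing does not remove this error.

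**The case against.** The strongest reply is that section 5.1.2 targets change, and a constant site shift cancels in within-patient change. This stands. The exposure comes from the unpaired test in section 11.6. That section does use each patient's own pre-study value as a control, but it says so only for the tetanus/PPD assay.

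The second reply is that any numerical size is assumed. This also stands. A reader might take the 54% effective sample as the expected loss, but it needs a shift of 2 SD. At 0.25-0.5 SD the loss is negligible, and the documents do not say which applies.

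Some stronger readings are tempting but not supported:

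- **That kits differ by site.** They vary by assay and batching. Nothing says that some patients get one kit and others another, or that values will be pooled. Luminex and CBA could both be run on every serum sample, and the 10-plex/25-plex choice concerns supernatants. What the documents show is two unreconciled statements and no rule fixing the kit across a patient's visits.
- **That the shipped blood is certainly unseparated.** This is inferred from a short instruction that lists no processing step, and section 11.5 is not limited to one site.
- **That no cells can be obtained from that site.** Only the CPT step is ruled out. Section 11.6 also describes isolating cells from blood by other routes, and 30 mL of EDTA blood is ample next to 15-18 mL.
- **That plasma and serum are confused.** Section 4.2 and a label example in section 11.5 mention plasma, but section 11.5 draws both kinds of tube, so this is weak.

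It is also fair to say that requiring CPT tubes, local separation and frozen shipment at every site is a debatable trade-off. The documents do not show that it beats central processing for the functional assays.

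**Conclusion.** The concern holds as two separate problems, both confined to the secondary immune results. The collection instructions for one site conflict with the general procedure, and the only stated immune test has no site term. That adds noise if handling shifts the readings, and bias if the site mix also differs by response. Separately, the serum cytokine platform is stated in two ways, the supernatant panel depends on batching, and nothing keeps a patient's visits on one kit. This second problem would survive a paired analysis.

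Neither effect can be sized from the documents. On the assumed shares of 20-30%, the effective sample for pooled levels runs from about 99% of nominal (0.25 SD shift) down to 54% (2 SD). The primary response endpoint and its decision rule are untouched. The change is still worth making, because it is cheap and the affected results are a listed secondary objective and endpoint.

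**What to change.** 1. Reconcile Appendix IX with section 11.5, so that each site's tubes, processing steps and method of obtaining cells are stated, and record draw-to-processing time for every sample at every site.
2. In section 11.6, name one platform and panel for serum cytokines and one for culture supernatants, and remove the conflicting or batch-dependent alternatives.
3. Run all of a patient's archived samples for a given assay on one plate and one lot.
4. Replace the unpaired t test with an analysis of within-patient change (paired, or a mixed model) with site as a stratum, and define the groups for the comparison by response. Do not pool absolute levels across handling methods without a site term.

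The cost is a revised laboratory instruction, a little more analysis work and less freedom in batching. Samples already shipped under Appendix IX remain usable for within-patient change, provided a patient's samples were all handled the same way.
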